9.5.3 TIME TO LOSS OF EFFICACY

Lack of efficacy is defined as discontinuation from the study or study drug for lack of efficacy. The time will be defined as the following:

Discontinuation Date – Randomization Date + 1

Time to loss of efficacy will be analyzed via a log-rank model with treatment effects. The time-to-event “survival” curve will be presented using the Kaplan-Meier method. Median time-to-event and the 95% confidence interval of the median times will be presented, if estimable. In these time-to-event analyses, subjects who do not have the event during the entire study will be censored at Day 84 (end of Week 12 day).

9.5.4 CHANGE FROM BASELINE TO LAST WEEK OF TREATMENT IN PGI-I SCALE

Change from baseline in PGI-I will be analyzed via similar methods to those for the primary efficacy variable.

9.5.5 CHANGE FROM THE OPEN-LABEL TITRATION PHASE BASELINE TO THE LAST WEEK OF TREATMENT OF THE DOUBLE-BLIND TREATMENT PHASE IN WPAI SCORE

This variable will be analyzed via similar methods to those for the primary efficacy variable.

9.5.6 CHANGE FROM THE OPEN-LABEL TITRATION PHASE BASELINE TO THE LAST WEEK OF TREATMENT OF THE DOUBLE-BLIND TREATMENT PHASE IN EUROQOL GROUP EQ-5D-5L SCORE

This variable will be analyzed via similar methods to those for the primary efficacy variable.

9.5.7 RESCUE MEDICATION USAGE (NUMBER OF DAYS) DURING THE DOUBLE-BLIND TREATMENT PHASE.

Rescue medication usage will be collected from the electronic diaries.

There were technical issues with the electronic diaries for rescue medication usage. For example, subjects entered data multiple times (more than 30 times per day in some cases), possibly due to poor internet connectivity. As a result of these issues, the total rescue dosage was not reliable. Therefore, the electronic diary source of rescue medication usage will be used only to derive the number of days that rescue medication was used.

The number of days that rescue medication is used will be normalized on a weekly basis in the analysis (i.e., number of days that rescue medication is used per week) based on the electronic diaries. Specifically, number of days that rescue medication is used per week will be derived as $7*(X/Y)$, where X=total number of days that rescue medication is taken during the week and Y=total number of days that diaries are available in that week. This variable will be analyzed via similar methods used to analyze the primary efficacy variable.

9.6 EXPLORATORY EFFICACY OUTCOMES

The exploratory efficacy endpoints are as follows:

- Percentage of subjects with a 70% or greater decrease in API from the Open-Label Titration Phase baseline to Week 12 of the Double-Blind Treatment Phase
- Change from baseline to Week 12 of the Double-Blind Treatment Phase in Clinical Global Impression of Improvement (CGI-I) scale (as assessed by the Investigator).

9.6.1 PROPORTION OF RESPONDERS WITH A $\geq 70\%$ REDUCTION FROM THE OPEN-LABEL TITRATION PHASE BASELINE TO WEEK 12 OF THE DOUBLE-BLIND TREATMENT PHASE IN API SCORE OVER TIME

Percent reduction from the Open-Label Titration Phase baseline in NRS score to a given post-baseline Week will be derived as $100 * (\text{Titration baseline pain score} - \text{Post-Baseline API}) / (\text{Titration baseline pain score})$. A subject is a responder if the percent reduction is at least 70%. A subject with missing API for a given post-baseline week will be considered as a non-responder.

This variable will be analyzed using the chi-square test. The percentages, the difference of the percentages, and the two-sided 95% confidence interval of the treatment difference will be presented. The 95% confidence intervals of the treatment difference will be calculated using normal approximation.

9.6.2 CHANGE FROM BASELINE TO WEEK 12 IN CGI-I SCALE

Change from baseline in CGI-I will be analyzed via the similar methods to those for the primary efficacy variable.

9.7 INTERIM ANALYSES

No interim analyses will be performed.

9.8 ADJUSTMENTS FOR MULTIPLICITY

There is only one primary comparison for the study. The clinical efficacy endpoints listed below are listed in order of hierarchical importance:

1. The primary efficacy endpoint, which is change from baseline in WAAPI at last week of treatment;
2. Change from baseline in the weekly average of daily WPI scores at last week of treatment of the Double-Blind Treatment Phase, based on an NRS-11;
3. Percentage of subjects with a 50% or greater decrease in API from the Open-Label Titration Phase baseline to the last week of treatment of the Double-Blind Treatment Phase;
4. Percentage of subjects with a 30% or greater decrease in API from the Open-Label Titration Phase baseline to the last week of treatment of the Double-Blind Treatment Phase;
5. Time to loss of efficacy, defined as discontinuation from the study or study drug for lack of efficacy;
6. Change from baseline to last week of treatment of the Double-Blind Treatment Phase in PGI-I scale (as assessed by the subject);
7. Change from baseline to last week of treatment of the Double-Blind Treatment Phase in WPAI score;
8. Change from baseline to last week of treatment of the Double-Blind Treatment Phase in EuroQoL Group EQ-5D-5L score; and
9. Rescue medication usage during the Double-Blind Treatment Phase.

The null hypotheses of no treatment difference for the above endpoints will be tested at a two-sided significance level of 0.05 in the order specified. To protect the family-wise two-sided p-value at the 0.05 significance level, the treatment superiority for an endpoint cannot be claimed, unless the superiority claims for all prior endpoints in the list, if any, have been established.

9.9 POWER AND SAMPLE SIZE JUSTIFICATION

A sample size of 170 subjects per treatment group will provide over 90% power to detect a treatment difference at a two-sided 5% significance level. In the sample size calculation, a treatment difference of 0.7 units and an SD of 2 (or a standardized effect of 0.35) for the primary efficacy variable were assumed.

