8.3. Method of Assigning Subjects to Treatment Groups

Randomization will be used to avoid bias in the assignment of subjects to treatments, to increase the likelihood that known and unknown subject attributes (e.g., demographics, baseline characteristics) are evenly balanced across treatment groups, and to enhance the validity of statistical comparisons across

treatment groups.

Subjects who provide written informed consent will be assigned a unique number in the screening process. This number will be used to identify the subject throughout the study.

Subjects who meet the eligibility criteria will be randomized in a 1:1 ratio (Group 1: active CAM2038 SC injections or Group 2: placebo SC injections). Randomization will be stratified based on double blind dosing regimen. Subjects randomized at a titration dose of either 4, 8 or 12 mg will remain on weekly doses. Subjects randomized at a titration dose of 16, 24, or 32 mg will transition to monthly dosing.

Therefore, there will be four different dose types.

- A1 – Active weekly
- B1 – Placebo weekly
- A4 – Active monthly
- B4 – placebo monthly

Due to the size of the study, it is expected that subjects will be balanced for various other baseline factors, including age.

Once any subject number or randomization number is assigned, it cannot be reassigned to any other subject. This study will use central randomization, as described in Section 9.2.

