11.4. Determination of Sample Size

It is estimated that 170 subjects per treatment group will provide 90% power with a 2-sided test at a 5% significance level and standard deviation of API at Week 12 of 2.0 to detect a treatment effect of 0.7 unit (or a standardized effect of 0.35) in change from baseline in the WAAP scores at Week 12 (Double-Blind Phase). Considering a titration success rate of 60%, this study will enroll approximately 875 subjects to obtain 340 subjects achieving a successful dose in order to be randomly assigned to study drug treatment in the Double-Blind Phase.

Additional statistical details will be outlined in the SAP.

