5.2 MODIFIED INTENT-TO-TREAT POPULATION

The modified Intent-to-Treat (mITT) Population will consist of all randomized subjects with the exception of all subjects from Sites 068 and 077 due to persistent non-compliance.

Site 068:

A for-cause audit was performed on 02 Oct 2017 for Site 068 in response to a quality event. There were several Critical and Major observations noted during the audit; the deficiencies noted during the audit were based on a random sampling of data. Below are some of the observations noted:

The Critical observations were:

- Subject signatures on revised informed consent forms could not be confirmed as authentic.
- The data on subject diaries could not be attributed to the subjects themselves.
- Subject eligibility could not be confirmed with provided source documents.

The Major observations were:

- Source documentation provided was found to be inadequate and/or unreliable.
- There was inadequate accountability and review by site staff of subject diaries.
- There was inadequate reporting and assessment of adverse events.
- The site did not have appropriate research staff based on qualification, training and experience.

The above observations have led to uncertainty in the integrity and reliability of the data collected at this site. Therefore, the data will not be included in the efficacy analysis.

Site 077:

Multiple audits, including a for-cause audit and several quality visits, were conducted by the Sponsor, Medpace (the contract research organization [CRO]) and third-party auditors, due to the Site 077 enrolling a large number of subjects into the study. These audits and quality visits led to several Critical and Major observations noted below:

The Critical observations were:

- Not all subjects spoke, read or comprehended English, and as a result, the Informed Consent (IC) process and every study visit was conducted in Spanish or through an interpreter/impartial witness. This was not permitted in the protocol and was not documented in the source documentation.
- The study staff were unblinded throughout the entire study. The study staff who administered the investigational product also performed the protocol-required assessments at each visit.
- Source documentation was manually changed, allowing several subjects to meet inclusion and exclusion criteria for the study.

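### SAP 9.9 claims over 90% power for 170 per group; its inputs give 89.6%, and the figure was not updated when two sites left the primary population

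*SAP*

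**What the plan says.** SAP 9.9 states: "A sample size of 170 subjects per treatment group will provide over 90% power to detect a treatment difference", "at a two-sided 5% significance level". On the inputs it says that "a treatment difference of 0.7 units and an SD of 2 (or a standardized effect of 0.35) for the primary efficacy variable were assumed".

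Protocol 11.4 uses the same inputs but makes the weaker claim: "It is estimated that 170 subjects per treatment group will provide 90% power". It describes the SD as a "standard deviation of API at Week 12 of 2.0 to detect a treatment effect of 0.7 unit".

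Protocol section 7 makes clear that 170 per group (about 340 in all, at about 85 sites) counts randomized subjects. Protocol 11.2 makes the ITT population, all randomized subjects, the primary efficacy population.

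SAP 5.2 and 9.3 replace this with the mITT population, which is all randomized subjects except those at Sites 068 and 077. The SAP explains the audits of Site 077 as "due to the Site 077 enrolling a large number of subjects into the study". No count is given for either site. Section 9.9 refers neither to the mITT population nor to the exclusion.

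**The concern.** Two things do not fit. First, the SAP turned the protocol's 90% into *over* 90% with no change of input. Second, the sample size in 9.9 describes a different set of subjects from the one the SAP analyses. Both sections are in the same final SAP version, dated 31 August 2018, about eleven months after the Site 068 audit of 2 October 2017. The exclusion was therefore known when 9.9 was finalised.

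What is at stake is interpretation. No test, significance level or decision rule depends on the power figure. A reader of a non-significant result would, however, judge the trial's sensitivity against a figure that belongs to the all-randomized target and not to the primary analysis.

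**Working it through.** **Inputs.** From SAP 9.9: n = 170 per group, difference 0.7, SD 2, two-sided alpha 0.05. From Protocol 8.3: 1:1 allocation. The standardized effect is d = 0.7 / 2 = 0.35.

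**Step 1: the plan's own figure.** The noncentrality is d × √(n/2) = 0.35 × √85 = 3.227.

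- Normal approximation: Φ(3.227 − 1.960) = Φ(1.267) = 89.7%.
- Noncentral t, 338 degrees of freedom, critical value 1.967: 89.6%.

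The protocol's 90% is therefore reproduced as rounding. The SAP's *over 90%* is not, though it misses by only 0.3 to 0.4 percentage points. A one-sided 5% test would give 94.3%, but both documents specify a two-sided test.

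**Step 2: the number needed for 90%.** n = 2 × (1.960 + 1.282)² / 0.35² = 171.5, so 172 per group by the normal approximation. The t test needs 173 (power 90.08%). The shortfall is two or three subjects per group.

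**Step 3: the site exclusion.** Suppose 170 per group were randomized and the exclusion removes the same share from each arm. The shares are assumptions, because the documents give no counts. The 2.4% row is what two average-sized sites would represent: 2/85 = 2.4%, or 8 of 340 subjects at 340/85 = 4 per site, leaving 166 per group.

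| Share removed (assumed) | n per group | 0.35 × √(n/2) | Power, t | Power, normal |
|---|---|---|---|---|
| 0% | 170 | 3.227 | 89.6% | 89.7% |
| 2.4% | 166 | 3.189 | 88.9% | 89.0% |
| 5% | 161.5 | 3.145 | 88.0% | 88.2% |
| 10% | 153 | 3.061 | 86.2% | 86.5% |
| 20% | 136 | 2.886 | 82.0% | 82.3% |

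**Step 4: the baseline covariate.** The primary model in SAP 9.3 adjusts for baseline WAAPI. If the SD of 2 is unadjusted and the outcome has correlation ρ with baseline, the residual SD is 2 × √(1 − ρ²). No ρ is stated in either document. Noncentral t results for assumed values are:

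| ρ (assumed) | 170 per group | 153 per group (10% removed) |
|---|---|---|
| 0 | 89.6% | 86.2% |
| 0.13 | 90.1% | 86.8% |
| 0.2 | 90.7% | 87.6% |
| 0.4 | 94.0% | 91.5% |

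A very small correlation closes the gap in Step 1. A 10% exclusion needs a larger one.

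**The case against.** The strongest reply is that the arithmetic gap is a rounding matter. The shortfall is under half a point on an assumed SD, the protocol says 90% from the same inputs, and only one word in 9.9 is wrong. That is correct, and the wording alone would hardly merit a comment.

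A reader might go further and infer that 170 per group can never exceed 90%, or that the mITT population cannot have the stated power. The documents do not support either reading:

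- The 89.6% is for an unadjusted comparison, whereas the planned model is adjusted. Step 4 shows that an assumed modest correlation takes the figure past 90%.
- Neither document reports how many subjects were randomized. If more than 340 were, the mITT set could still hold 170 or more per group. With 10% excluded, keeping 173 would take 173 / 0.9, or about 193 randomized per group.

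The size of the loss is also open. The description of Site 077 concerns subjects enrolled, and Protocol 11.4 uses that verb for the roughly 875 who enter before titration, so it need not mean a large share of those randomized. SAP section 12 implies that the two sites were among those enrolling more than 10 subjects, which suggests that they were above a trivial size but does not give a number.

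Finally, it would be unfair to say that the plan ignores dropout. Protocol section 7 allows discretionary replacement of subjects who discontinue, and SAP 9.3 keeps collecting efficacy data after study drug is stopped and uses all observed weeks. There is no numerical dropout allowance in the calculation, but that is separate from the site exclusion. Replacement is described for subjects who discontinue, not for excluded sites, and the repeated-measures model recovers nothing from a site whose data are removed.

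What remains after these replies is that 9.9 quotes a figure for one population while the SAP's primary analysis uses another.

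**Conclusion.** Wrong as written, minor. On the stated inputs, 170 per group gives 89.6% (t) or 89.7% (normal), so *over 90%* should read *about 90%*. The more useful criticism is that the statement was not carried over to the mITT population that the same SAP makes primary. If about 170 per group were randomized and the exclusion falls equally on both arms, unadjusted power is between 88.9% and 82.0% for assumed losses of 2.4% to 20%. Those shares illustrate the effect and do not estimate it. Over-enrolment or the covariate could offset the loss partly or fully, so a serious loss of power has not been shown. The validity of the primary test is not affected.

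**What to change.** In SAP 9.9:

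1. Replace the claim of more than 90% with approximately 90% (89.6%) for 170 randomized subjects per group, under the stated difference, SD and two-sided level.
2. Add the actual number per group in the mITT population and the power at that number under the same assumptions.
3. If any variance reduction from baseline WAAPI is counted, state the assumed correlation and whether the SD of 2 is before or after adjustment. The protocol describes it as the SD of API at Week 12, and the SAP as that of the primary efficacy variable.

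This costs a few sentences. It needs no extra enrolment and no change to the analysis. The only downside is that the stated figure may be slightly less favourable.

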10. SUMMARIES OF MEASURES OF SAFETY

Safety analyses will be performed for both the Primary and Supportive Safety Populations. Safety evaluations will be based on the incidence, intensity, and type of adverse events (AEs), as well as on clinically significant changes in the subject's physical examination, vital signs, electrocardiogram (ECG), clinical laboratory results, and injection site examination. Safety variables will be tabulated and presented by study drug received.

Because there is no pre-specified safety outcome defined in terms of AEs, clinically relevant laboratory parameters, or vital signs in the Double-Blind Treatment Phase of the study, any formal comparisons between the treatment arms with respect to specific safety parameters will be post hoc.

10.1 EXTENT OF EXPOSURE

Summary statistics (number and percentage) of weeks of exposure to study drug (i.e., from date of initial injection to 4 weeks after the last injection for q4w, or 1 week for q1w) will be tabulated by treatment group.

10.2 ADVERSE EVENTS

All AE and serious adverse event (SAE) terms recorded on the CRFs will be coded by primary system organ class (SOC) and will be mapped to a preferred term using the MedDRA. The Investigator will assess AE severity and relationship to the study treatment.

A treatment-emergent adverse event (TEAE) is defined as any AE with an onset date on or after the first dose of CAM2038, or any ongoing event on the date of first dose that worsens in severity after the first dose of CAM2038. Only TEAEs with an onset date prior to date of last dose plus 30 days will be tabulated in summary tables. For the purpose of calculating TEAEs and inclusion in summary tables, incomplete onset dates will be imputed as detailed in Appendix A.

AEs will be summarized by the number and percent of subjects in each primary SOC and preferred term, and subjects will be counted only once for each primary SOC and each preferred term. Summary tables of AEs by primary SOC, preferred term, and intensity will be provided. If a subject has more than one AE coded to the same preferred term, the subject will be counted only once for that preferred term by using the event with the highest intensity. Similarly, if a subject has more than one AE within a primary SOC category, the subject will be counted only once in that SOC category by using the event with the highest intensity.

AEs by primary SOC, preferred term, and relationship to study drug will be provided as well. If a subject has more than one AE coded to the same preferred term, the subject will be counted only once for that preferred term by using the most related event. Similarly, if a subject has more than one AE within a primary SOC category, the subject will be counted only once in that primary SOC category by using the most related event.

In addition, SAEs by primary SOC and preferred term will be provided. Deaths and SAEs will be summarized similarly to AEs. All adverse event tables will also include the total number of events, counting multiple events per subject.

AEs, Injection-related AEs, and other (non-injection related) AEs will be presented by treatment group and overall. Summaries of these AE subsets will be presented for the following categories:

- Study drug related AEs
- AEs by intensity
- AE relationship to injection
- Possibly study drug related AEs, by intensity
- AEs reasonably related to injection, by intensity
- SAEs
- AEs that led to discontinuation
- SAEs that led to discontinuation
- AEs occurring in $\geq 5\%$ of any treatment group, by preferred term

In the AE summary, preferred terms within each SOC will appear in alphabetical order.

Frequencies for deaths and hospitalizations will also be summarized by treatment group and overall.

Other safety analyses will be performed as appropriate.

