4.4 RANDOMIZATION AND BLINDING

Randomization will be used to avoid bias in the assignment of subjects to treatment, to increase the likelihood that known and unknown subject attributes (e.g., demographics, baseline characteristics) are evenly balanced across treatment groups, and to enhance the validity of statistical comparisons across treatment groups.

During the Open-Label Titration Phase, subjects will be dosed with CAM2038 q1w until a stabilized dose and adequate analgesic effect has been achieved for at least 2 consecutive weeks prior to randomization to the Double-Blind Treatment Phase, in accordance with pre-defined randomization criteria. Subjects whose pain is controlled on 4 mg, 8 mg or 12 mg CAM2038 q1w during the Open-Label Titration Phase will be maintained on 4 mg, 8 mg or 12 mg CAM2038 q1w, or corresponding placebo, during the Double-Blind Treatment Phase. Subjects whose pain is controlled on 16 mg, 24 mg or 32 mg CAM2038 q1w during the Open-Label Titration Phase will be transitioned to CAM2038 64 mg, 96 mg or 128 mg q4w, or corresponding placebo, during the Double-Blind Treatment Phase. Subjects will be randomized to either active CAM2038 or placebo control in a 1:1 ratio within each of the q1w or q4w regimens.

Under normal circumstances, the blind will not be broken until all participants have completed treatment. In case of emergency, and only if the information is required by the Investigator to ensure subject's safety in managing a medical condition, the treatment may be unblinded at the site by using a code-break module. The code-break module will be provided by the Sponsor or designee. If possible, the Investigator should contact the Sponsor prior to unblinding and after any actions have been taken. Whenever a treatment sequence is prematurely unblinded, the reason, date and time of the unblinding, and the individual who broke the blind, must be documented. Individual code breaks will result in withdrawal of the participant from the study.

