5.4 SAFETY POPULATION

The Safety Population will include all subjects who have received any dose of study medication. Analyses based on this population will group subjects according to the treatment they received rather than the treatment they were randomized to receive. All safety analyses will use the Safety Population.

In the primary safety summaries, data for Sites 068 and 077 mentioned in [Section 5.2](#) will be excluded, due to an inability to verify compliance with adverse event reporting requirements, leading to possible under-reporting of adverse events. However, supportive safety summaries will include the data from Sites 068 and 077.

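### SAP 10.2 starts the TEAE window at the first open-label CAM2038 dose and tabulates by treatment group with no phase split, so the by-arm AE tables do not give the randomised comparison

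*SAP*

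**What the plan says.** SAP Section 3 puts both the titration and double-blind phases in scope. SAP 4.4 says "During the Open-Label Titration Phase, subjects will be dosed with CAM2038 q1w until a stabilized dose and adequate analgesic effect has been achieved", after which subjects are randomised 1:1 to CAM2038 or placebo. Protocol 8.1.3 places the first CAM2038 dose on Day 1 of titration.

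SAP 10.2 defines the window: "A treatment-emergent adverse event (TEAE) is defined as any AE with an onset date on or after the first dose of CAM2038" (or worsening after it). It tabulates events with onset before the last dose plus 30 days, without saying the last dose of which product. The layout is: "AEs, Injection-related AEs, and other (non-injection related) AEs will be presented by treatment group and overall".

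Two sentences come close to an attribution rule. SAP 5.4 says "Analyses based on this population will group subjects according to the treatment they received rather than the treatment they were randomized to receive", and SAP Section 10 says "Safety variables will be tabulated and presented by study drug received". SAP 5.4 admits anyone with any dose of study medication, so subjects who fail titration are in the Safety Population.

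On counting, for repeated events under one term SAP 10.2 says "the subject will be counted only once for that preferred term by using the event with the highest intensity". A parallel rule uses the most related event. It adds: "All adverse event tables will also include the total number of events, counting multiple events per subject".

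**The concern.** A placebo-arm subject has received both CAM2038 and placebo. Grouping subjects by treatment received does not say which drug governs, and tabulating by study drug received carries no onset-date rule. Protocol 11.3.7 adds no phase split. The by-arm AE tables can therefore be built in several ways from the same text, and none of them isolates what happened after randomisation.

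The counting rules add to this. A severe titration event can set a subject's intensity category, and a milder double-blind event under the same term then disappears from the subject-level row. It survives only in the event totals. The table of AEs in at least 5% of any treatment group inherits the same window.

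What is at stake is a descriptive comparison. Safety and tolerability of CAM2038 is a secondary objective in Protocol 5.2, and the AE tables are a main part of how it is reported.

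**Working it through.** The plan states no AE figure to reproduce. The check is one of text, followed by illustrations on assumed rates.

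**Share of the window spent in titration.** Protocol 7.4 requires at least 2 weeks on a stable CAM2038 dose before randomisation, and Protocol 6.1 allows up to 10 weeks of titration. Take the last dose as the last double-blind injection: Day 78 for q1w (77 days after the first) and Day 57 for q4w (56 days after). Share = titration days / (titration days + days to last injection + 30).

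- 10 weeks: 70/177 = 40% (q1w); 70/156 = 45% (q4w).
- 2 weeks: 14/121 = 12% (q1w); 14/100 = 14% (q4w).

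**Reading A: subjects columned by randomised arm.** Assume double-blind incidence of 30% active and 20% placebo, and titration incidence pT equal in both arms. Under independence, column incidence = 1 - (1 - pT)(1 - pDB), so the difference is (1 - pT) x 10 points. As a sensitivity case, let AEs cluster within subjects at an odds ratio of 3 with the same margins. For placebo at pT = 30% this means 10% with AEs in both phases, 20% in titration only, 10% in double-blind only and 60% in neither: (0.10 x 0.60)/(0.20 x 0.10) = 3.

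| pT | Independence: active vs placebo | Difference | Odds ratio 3: active vs placebo | Difference |
|---|---|---|---|---|
| 10% | 37.0 vs 28.0 | 9 | 34.7 vs 26.1 | 8.6 |
| 30% | 51.0 vs 44.0 | 7 | 45.9 vs 40.0 | 5.9 |
| 50% | 65.0 vs 60.0 | 5 | 59.4 vs 55.8 | 3.6 |

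Placebo subjects whose only AE was in titration, as a share of placebo subjects shown with an AE:

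- Independence: 8.0/28.0 = 29%, 24.0/44.0 = 55%, 40.0/60.0 = 67%.
- Odds ratio 3: 6.1/26.1 = 23%, 20.0/40.0 = 50%, 35.8/55.8 = 64%.

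**Reading B: events columned by drug at onset.** Consider randomised subjects only. The CAM2038 column then holds all 340: half with both phases on drug, half with titration only. Its incidence under independence is half of [1 - 0.70(1 - pT)] plus half of pT. The placebo column stays at 20%.

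- pT 10%: (37.0 + 10.0)/2 = 23.5%; difference 3.5 points.
- pT 30%: (51.0 + 30.0)/2 = 40.5%; difference 20.5 points.
- pT 50%: (65.0 + 50.0)/2 = 57.5%; difference 37.5 points.

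**Reading C: arm columns, with titration failures added to CAM2038.** Failures received only CAM2038, so SAP 5.4 and Section 10 allow this. Protocol 11.4 assumes 60% titration success: 340/0.60 = 567 titrated, 567 - 340 = 227 failures. CAM2038 incidence = (170 x active rate from Reading A + 227 x failure rate)/397.

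- pT 10%, failures 10%: (62.9 + 22.7)/397 = 21.6%, against 28.0%; difference -6.4.
- pT 10%, failures 60%: (62.9 + 136.2)/397 = 50.2%; difference +22.2.
- pT 30%, failures 30%: (86.7 + 68.1)/397 = 39.0%, against 44.0%; difference -5.0.
- pT 30%, failures 60%: (86.7 + 136.2)/397 = 56.1%; difference +12.1.

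The 227 is uncertain. Protocol 11.4 speaks of enrolling about 875, while the synopsis and Section 7 speak of screening 875. If all 875 entered titration, failures would be 875 - 340 = 535, which does not fit the 60% rate. The pT = 10% results would then be (62.9 + 53.5)/705 - 28.0% = -11.5 points and (62.9 + 321.0)/705 - 28.0% = +26.5 points. All counts are before the site exclusion in SAP 5.4 ("In the primary safety summaries, data for Sites 068 and 077").

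**The case against.** The strongest defence is that the window is deliberate. Protocol 4.2 says CAM2038 safety will be evaluated from titration onwards, and SAP Section 3 includes titration. That stands: opening the window at the first CAM2038 dose is not itself the error. The defect is using that window, undivided, in tables by arm.

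A second defence is that tabulating by study drug received already assigns titration events to CAM2038. It may be meant so, but the text does not say it, and Reading B shows the result would still not be the randomised comparison.

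A third is that Appendix A moves partial AE dates to one side or the other of randomisation, which suggests a split was contemplated. That is an inference. No table in SAP Section 10 is defined by it.

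On stakes, much of the objection holds. SAP Section 10 calls any formal safety comparison post hoc, so no prespecified test is touched. SAP Section 6 lists all data. The protocol objective concerns CAM2038 and does not mention placebo, SAP 4.1 lists no safety objective, and laboratory, ECG, withdrawal-scale and other summaries are separate.

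A reader might infer that the active-placebo difference must be diluted, or that titration failures can appear only in the overall column. The documents support neither. Failures can be placed under CAM2038, and the difference can then rise, fall or change sign.

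**Conclusion.** The point holds as a defect in how the AE tables are specified, and it should be corrected. As written, no reading of the by-arm tables gives the double-blind comparison of CAM2038 with placebo. Columned by arm, an assumed 10-point difference shrinks to between 9 and 5 points under independence, or 8.6 to 3.6 with clustering. Columned by drug at onset, it runs from 3.5 to 37.5. With about 227 failures under CAM2038 and 10% titration incidence in randomised subjects, it runs from about -6 to +22.

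The AE rates, the odds ratio and the number of failures are all assumptions, and they show sensitivity only. The documents do not support a claim that efficacy conclusions, power or a formal safety test are compromised, or that AE data would be lost.

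**What to change.** In SAP 10.2, define two sets.

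1. Titration TEAEs: onset or worsening from the first CAM2038 dose to before the first double-blind injection, in one CAM2038 column for all treated subjects, including those never randomised.
2. Double-blind TEAEs: onset or worsening from the first double-blind injection to the last double-blind dose plus 30 days, by arm, in randomised and dosed subjects.

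Apply the once-per-term, highest-intensity and most-related rules within each set.

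Align Appendix A. It now sends completely missing onset dates, and same-year dates lacking a month, to the randomisation date. After the split, that would by default turn titration events into double-blind ones. It also mixes randomisation and first dose as anchors, and has no anchor for never-randomised subjects.

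Add a table note that early double-blind AEs in the placebo arm may reflect residual buprenorphine. Protocol 8.7 gives up to 2 weeks for receptor dissociation after q1w. With nominal injections at Weeks 10 and 11, that reaches roughly through the first double-blind week. The split does not remove this carry-over.

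The change needs SAP wording and table shells only, since dose and AE dates are already collected. The cost is one more set of AE tables.
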